Each participant will be assigned a unique identification number once it has been determined that the person meets the inclusion criteria and has signed the consent form and HIPPA authorization form. The unique number will be used to identify all data sets for the individual participant. De-identified information obtained during this study will be released to requesting agencies only with a written release of information from the participant. The results of this research may appear in scientific publications but the participants' names will not be used. All data will be maintained in a research folder in a locked cabinet in the David M. Crowley Research and Rehabilitation Laboratory. The UT Southwestern Institutional Review Board is responsible for assuring that participants' rights are respected. Members of the staff may review records for audit purposes. That review will take place at The Department of Physical Therapy.

13. Potential Benefits:

It is anticipated that the application of this orthosis will result in an immediate improvement in gait parameters (temporal and spatial) as well as long term improvements in activity and gait tolerance as well as balance and strength.

14. Biostatistics:

The proposed design thus consists of two treatment groups ("between" effect) with 8 patients (subjects)/group studied over 3 test sessions ("within" effect). At each data point, nine classes of measures are to be obtained, e.g., the 6-minute walk test, computerized gait analysis, etc. Some of these classes may yield more than one measure. We propose four groups of analyses.

Intent to treat analysis.

Not all patients who initially consent and are randomized may complete the study. We plan to compare (a) those that finish with those who do not finish to see if they differ with respect to any of the dependent variables and (b) the proportions of those who do not finish to see if they are equally divided among the groups. The former will be compared by means of *t*-tests or its nonparametric

counterpart, the Mann-Whitney U, depending upon how well normality assumptions are met. The latter will be compared by means of chi-square or Fisher exact test depending upon sample size. Preliminary psychometric analyses.

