We feel it important to evaluate the relations among the various classes of dependent variables by intercorrelating them to infer their structure, e.g., how many dimensions do they span and are any sufficiently redundant so they can be combined. This involves standard item analysis and exploratory factor analysis. Similar analyses will be performed on the scores obtained from the inclusion measures and other demographics, e.g., can the Hoehn and Yahr scores be combined with other measures to obtain a composite impairment measures that can serve as a better covariate.

Analysis of observed measures

If all patients who complete the study do so without missing any of the test sessions, ordinary repeated measures analysis of variance (ANOVA) will be used to evaluate the main effect of groups, the main effect of testing sessions, and their interaction. Planned comparisons will be employed comparing (a) groups G1 and G2 with each other. This involves comparing what in effect are two control conditions with each other and their average against the active treatment condition. This will be done as a series of univariate tests.

Next, we will examine the effects of covariates such as age of onset and impairment as inferred through the Hoehn and Yahr scale and other measures, again in a univariate manner.

We will then perform a multivariate analysis of variance (MANOVA) to test the null hypotheses that differences on the three effects of interest (groups, testing session, and their interaction) are all nonsignificant across the set of dependent variables.

It is quite likely that there will be missing data from patients who fail to attend one or more testing sessions. We will deal with this problem in two ways. One is to attempt to impute the missing data (see next subsection). The other is to use a mixed model (random regression) which does not require all data to be present, e.g. can analyze the testing effect using whatever data are present. This allows for the same univariate tests to be conducted, but makes multivariate testing extremely difficult to impossible with the data as obtained.

Analysis of imputed measures

Assuming there will be missing data, we will attempt to impute the missing data and perform the analyses as listed in the previous section, including the MANOVA, on these imputed data.

References

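### Nine classes of measures are tested one by one with no primary outcome, alpha, multiplicity rule or deciding analysis; even one measure per stated hypothesis carries a 16–26% chance of a false brace finding

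*Combined protocol and SAP*

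**What the plan says.** The three hypotheses in Section 1 are all brace-versus-control claims. They concern spatial and temporal gait parameters, gait kinematics and quality of life. Each names a domain, not a variable, and none is called primary. Walking endurance is part of the stated purpose but is in no hypothesis.

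On the amount of testing, Section 14 says "At each data point, nine classes of measures are to be obtained" and adds "Some of these classes may yield more than one measure". Section 8 numbers eight outcomes; the descriptions in Section 3 make nine only if the cognitive test is counted.

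Under Analysis of observed measures, each measure gets a repeated-measures ANOVA with tests of group, session and their interaction. On the planned comparisons the text says "This will be done as a series of univariate tests". Univariate covariate analyses follow, and after them: "We will then perform a multivariate analysis of variance (MANOVA) to test the null hypotheses that differences on the three effects of interest". Under Analysis of imputed measures the plan is to "perform the analyses as listed in the previous section, including the MANOVA, on these imputed data". The preliminary psychometric work asks of the measures "are any sufficiently redundant so they can be combined".

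On the contrast, the section opens with "The proposed design thus consists of two treatment groups", but the planned comparison is explained this way: "This involves comparing what in effect are two control conditions with each other and their average against the active treatment condition".

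In Section 4, baseline testing is done without orthoses and with the first set. The T2 and T3 rows give no brace condition.

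**The concern.** The trial makes three claims, and the plan does not say in advance which result would support or refute any of them. Every measure has at least two tests that could be read as a brace effect: the group main effect and the group-by-session interaction. The analyses are then repeated with covariates, possibly by mixed model, and on imputed data. With no alpha, no ordering and no deciding analysis, one significant result among many can be presented as support, and a reader has no stated error rate to judge it by.

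The contrast itself is also unsettled. Two control conditions averaged against an active one cannot be formed from two groups, so the only planned comparison in the plan cannot be carried out as described.

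**Working it through.** **No figure to reproduce.** The documents state no alpha, power, effect size or familywise error rate. The only design figures are group size and sessions, so the check asks what error rate the described testing produces.

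**Inputs from the documents.** Two groups, 8 per group, 3 sessions and nine classes (Section 14); three hypotheses (Section 1). Two tests per measure bear on the brace: group, F(1, 14), and interaction, F(2, 28). Session tests are left out because both groups receive the walking/exercise program.

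**Assumptions.** Alpha 0.05 per test, no brace effect, one measure per class or per hypothesis, normal outcomes that are equally correlated with each other. Outcome correlation is varied from 0 to 0.9.

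**Independent outcomes**, with k tests, 1 − 0.95^k:
- one measure per hypothesis, k = 3 × 2 = 6: 1 − 0.95^6 = 26%
- nine classes, k = 9 × 2 = 18: 1 − 0.95^18 = 60%
- the eight outcomes of Section 8, k = 16: 1 − 0.95^16 = 56%

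**Correlated outcomes**, by simulating the planned repeated-measures ANOVA at 8 per group with no effect. Entries are the chance of at least one significant group or interaction test when stable subject differences and session-to-session variation share the same correlation:

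| Measures | 0 | 0.5 | 0.7 | 0.9 |
|---|---|---|---|---|
| 3 (one per hypothesis) | 26% | 24% | 21% | 16% |
| 9 (one per class) | 60% | 48% | 38% | 24% |

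If only the stable differences correlate, the nine-measure figures are 53% at 0.7 and 49% at 0.9. The structure of the correlation therefore matters as much as its size. With 17 and 18 per group (35 in all) the nine-measure row is 60 / 48 / 37 / 24%, so group size does not drive the result.

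**What the MANOVA can do.** It comes after the univariate tests and is not made a condition for reading them. The plan itself expects missed sessions and says multivariate testing is then hardly possible on the data as obtained. With 16 participants and nine measures, the group test has 14 − 9 + 1 = 6 denominator degrees of freedom.

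**Cost of Holm over three outcomes.** The first step is 0.05 / 3 = 0.0167. For an unadjusted T3 comparison at 8 per arm (noncentral t, df 14), the noncentrality needed for 80% power is 3.01 at alpha 0.05 and 3.61 at 0.0167. Multiplying by √(1/8 + 1/8) = 0.5 gives detectable differences of 1.51 and 1.81 SD. Power for a 1.51 SD difference falls from 80% to 62%. In a T1-adjusted analysis, an effect with 80% power at 0.05 also falls to about 62%, for T1–T3 correlations from 0.3 to 0.7.

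**The case against.** The strongest reply is that the trial makes three domain claims, not nine. No passage says that any one significant result would count as support for the brace. Falls, steps per day, the Four Square Step Test, the 6-minute walk and the cognitive test are named in no hypothesis. This stands. A reader might infer that 60% is the trial's false-positive rate, but the documents do not support that; it applies only if any class may be cited. The hypothesis-matched 16–26% is the figure to lead with. It is a floor in the number of measures, because a class may yield several.

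A second reply is that the plan already contains a MANOVA and a search for redundant measures, and that the study is small and follows pilot work. Both elements deserve acknowledgement, but neither controls error as written. The MANOVA gates nothing, and the combining of measures has no criterion and no fixed resulting number of outcomes. Labelling all results exploratory, or making the MANOVA a true gate where the data allow, would be lighter remedies. The plan does neither and states directional hypotheses.

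Two further inferences should be resisted. Because baseline is tested with and without orthoses, a reader might suppose that G1 will be analysed both ways at T2 and T3, which would raise the error further. No passage says that both conditions are recorded or analysed at those visits; the condition is simply unstated. A reader might also expect T1 adjustment to pay for Holm. Compared like for like, with adjustment on both sides, the power loss remains.

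**Conclusion.** The concern holds. Section 14 does not identify the result that would decide any of the three hypotheses, does not control error across the tests it describes, and words its one planned comparison for a design the trial does not have. The size is 16–26% with one measure per hypothesis, three to five times a 5% level. It is roughly 24–60% if any of nine classes may be cited, depending on how strongly the outcomes correlate and in which component of variation. The figures rest on an assumed alpha of 0.05, no brace effect and one measure per class or hypothesis. They leave out the session tests, covariate analyses and imputed re-run. They are scenarios, not bounds. The absence of a primary outcome and of a rule for deciding does not depend on any of these assumptions.

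**What to change.** Before outcomes are compared by group, amend Section 14 as follows.

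1. Either designate a single primary outcome, or name one variable per hypothesis (for example GAITRite velocity, one specified kinematic variable and one named PDQ-39 score) and apply Holm at a stated two-sided family alpha.
2. Test each named outcome by one G1-minus-G2 contrast at T3 from the mixed model already planned, adjusted for its T1 value: the no-orthosis value for gait measures, the T1 score for PDQ-39.
3. State which brace condition decides each gait outcome at T3 (a matching entry is needed in Section 4).
4. Make that model the deciding analysis and the imputed run a sensitivity analysis. Report other outcomes, session effects and the MANOVA as exploratory estimates with intervals.
5. Rewrite the planned comparison as G1 versus G2.

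This is a change of wording and adds no visits. The cost of Holm is real: at its first step the unadjusted detectable difference at 8 per arm rises from 1.51 to 1.81 SD, and power falls from 80% to about 62%, with or without T1 adjustment. A single primary outcome avoids that loss, but the other two hypotheses then become secondary. The conflict between 8 per group and 35 in total should be raised as a separate point.

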This is a randomized, repeated measures, matched group study. There will be two groups of participants, 8 participants per group, 35 participants total from time of initial enrollment in this study. Group one (G1) will receive bilateral custom braces and a standardized home walking/exercise program. Group two will receive the standardized walking/exercise program without any brace or AFO. Subjects will be randomized upon enrollment in the study. At the time of consent, random drawing from concealed envelopes with red, blue or green chips will be done to determine group assignment. Subjects will be recruited through the Clinical Center for Movement Disorders at UT Southwestern Medical Center where patients with PD receive routine evaluation and follow-up. Subjects will be followed for 6 months during this study and outcome measures will be collected 3 times over the course of the study. Subjects will be seen every 3 months for the duration of the study for testing as well as for other visits as noted in the table below. Participants will not need to have insurance benefits for initial physical therapy evaluation and for ankle braces. All subsequent visits to the Crowley gait lab for assessments and brace adjustment will be provided at no cost to the participants.

Outcome measures

Testing Procedures:

6-Minute Walk Test: Each subject will be asked to walk at a self-selected velocity on level surfaces for 6 minutes. They will be allowed to use assistive devices if necessary.

Computerized Gait Analysis: Each subject will be asked to walk on a 12-16 foot long vinyl pad placed on the floor. The mat will record and analyze temporal and spatial gait parameters.

Observational Gait analysis: Gait will be evaluated using the Observational Gait Analysis system during over ground walking. A sample of the gait will be videotaped for detailed analysis.

Three-Dimensional gait analysis: Prior to testing, subjects will be outfitted with small retro-reflective markers secured to anatomical locations with easily removable tape. Once markers have been positioned properly, the subject will then be asked to walk up and down a level 15-foot walkway. Four walking trials will be recorded for averaging purposes.

Four Square Step Test: Balance while stepping in different directions will be assessed using this test. Skills such as stepping over an obstacle and stepping backwards are included in the test.

Falls data: Patients will be asked to fill out a fall log at home.

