Short Orientation-Memory-Concentration Test of Cognitive Impairment: Gross cognitive function will be tested using this brief questionnaire.

Daily Activity: Steps per day recorded from a pedometer the patients will wear for the week prior to each testing visit. Daily walking (steps/day) will be recorded throughout the study.

PDQ-39: The PDQ-39 is the most widely used Parkinson's Disease specific measure of health status. It contains thirty nine questions, covering eight aspects of quality of life. The instrument was developed on the basis of interviews with people diagnosed with the disease. It has been widely validated, and translated into over fifty languages.

4. Study Procedures: -

Screening, consent and randomization	Confirm medical diagnosis and medical history, assess sensation and range of motion. Consent process. Appointment made for casting.	60 minutes
Baseline Testing (T1)	Initial outcome measures completed with no	120 minutes

	orthoses and first set of orthoses.	
Visit 1 - 4 Month 1	Gait training session. Instruct in home walking program.	45 minutes
Visit 5 – Month 2		
Testing 2 (T2) – Month 3	All outcome measures completed.	120 minutes
Visit 6 and 7- Month 4 & 5	Gait training session.	45 minutes
Testing 3 (T3) – Month 6	All outcome measure completed	120 minutes

The gait training home program is outlined as follows:

- One to two bouts of focused walking per day. Regardless of the number of walking bouts, the goal is 30 minutes total per day.
- Increase the bouts by 2-5 minutes as tolerated working up to 30 minutes total
- Each subject will receive individualized tape walking protocol based on GAITRite data
- Each subject will receive standard instructions for a home exercise program and will receive handouts

5. Sub-Study Procedures:

There are no sub-studies.

6. Criteria for Inclusion of Subjects:

1. Confirmed diagnosis of Parkinson's Disease according to the UK brain bank criteria.⁵
2. Age between 30 and 85.
3. Measurable decrement in gait velocity (between 35 and 15 percent below age-predicted norms for self-selected walking velocity) as measured by the 6 MWT
4. Hoehn and Yahr stage 2-3.
5. Less than 10 full heel raises in single limb stance bilaterally.

7. Criteria for Exclusion of Subjects:

1. Body mass index greater than 40.
2. Passive dorsiflexion range of motion less than approximately neutral (90 degrees)
3. Any other uncontrolled health condition for which gait training is contraindicated
4. Self-report of > 1 fall/month

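### With 8 per group, the standard MANOVA of session and group-by-session on nine measures cannot be computed, and the plan sets no limit on the number of measures

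*Combined protocol and SAP*

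**What the plan says.** Section 14 (Biostatistics) describes two treatment groups "with 8 patients (subjects)/group studied over 3 test sessions". It adds: "At each data point, nine classes of measures are to be obtained", and then: "Some of these classes may yield more than one measure".

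Under the analysis of observed measures, univariate repeated-measures ANOVAs and covariate analyses come first. Then: "We will then perform a multivariate analysis of variance (MANOVA) to test the null hypotheses that differences on the three effects of interest". Those effects are group, session and group-by-session, each tested jointly over all the outcomes. The same MANOVA is to be repeated on imputed data.

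The form of MANOVA is not named: it could be doubly multivariate, or the averaged (multivariate mixed-model) form. An earlier paragraph proposes item and factor analysis to see whether outcomes are redundant enough to merge, but gives no target number or rule. The only obstacle to multivariate testing that the section mentions is missing data. No alpha, power, effect size or correlation is stated.

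**The concern.** A MANOVA needs at least as many error degrees of freedom as it has variables. In the doubly multivariate form, the variables for session and group-by-session are the measures multiplied by the session contrasts, which is a large number for 16 people.

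Group-by-session matters most here. T1 is the baseline testing visit, so a brace effect that develops over follow-up appears as a difference between groups in change. If the standard test of that effect cannot be computed, the analyst must choose after seeing data which measures to drop, which to merge, or which other statistic to use. The group test can be run, but if its power is low a null result says little about the brace.

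**Working it through.** **Inputs from the documents**
- Two groups of 8, so N = 16 (Section 14).
- Three sessions, so two contrasts per measure (Section 3: "outcome measures will be collected 3 times over the course of the study"; also Section 14).
- Nine classes of measures as a minimum (Section 14). Section 8 lists eight outcomes.

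**Assumed, because the documents are silent:** two-sided alpha 0.05, shifts of 1 SD, equal correlation ρ between measures. The plan has no power figure to reproduce.

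**Step 1: session and group-by-session, doubly multivariate form**
- Error df = 16 − 2 = 14.
- Nine measures: 9 × 2 = 18 contrasts. The 18 × 18 error matrix has rank at most 14, and a numerical check gave exactly 14. It is singular, so Wilks' lambda does not exist.
- Eight measures: 8 × 2 = 16 > 14, also singular.
- Computable only if 2p ≤ 14, that is p ≤ 7. The denominator df are 14 − 2p + 1, so seven measures leave 1 and three measures leave 9.
- With nine measures, N − 2 ≥ 18 requires N ≥ 20.

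None of this involves missing data, so imputing values cannot repair it.

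**Step 2: averaged form of the interaction**
The error matrix is 9 × 9 with 14 × 2 = 28 df and full rank. This test can be run, but it assumes multivariate sphericity.

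**Step 3: group test on nine measures (two-sample Hotelling T²)**
- F has 9 and 16 − 9 − 1 = 6 df; the 0.05 critical value is 4.10.
- T² = (14 × 9/6) × 4.10 = 86.1. Dividing by 8 × 8/16 = 4 and taking the root, significance needs an observed Mahalanobis distance of 4.64.
- For a 1 SD shift on all nine measures, D² = 9/(1 + 8ρ) and the noncentrality is 4D².

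| ρ | D² | Noncentrality | Power |
|---|---|---|---|
| 0 | 9.00 | 36.0 | 67% |
| 0.1 | 5.00 | 20.0 | 41% |
| 0.2 | 3.46 | 13.8 | 29% |
| 0.3 | 2.65 | 10.6 | 23% |
| 0.4 | 2.14 | 8.6 | 19% |
| 0.5 | 1.80 | 7.2 | 16% |
| 0.8 | 1.22 | 4.9 | 12% |

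Simulation (10,000 runs) gave 67.5%, 23.5% and 16.2% at ρ = 0, 0.3 and 0.5. For comparison, one t-test on one measure shifted by 1 SD has 46% power. With 6 completers per group, MANOVA power is 9% (ρ = 0.3) or 8% (ρ = 0.5). With 5 per group the denominator df are 10 − 9 − 1 = 0.

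**Step 4: other shift patterns, and a directional average score**
If k of nine measures shift by 1 SD, D² = [k − ρk²/(1 + 8ρ)]/(1 − ρ). The average score is a t-test on 14 df with noncentrality 2(k/9)/√[(1 + 8ρ)/9].

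| Measures shifted | ρ | MANOVA | Average score |
|---|---|---|---|
| 9 | 0.3 | 23% | 86% |
| 9 | 0.5 | 16% | 70% |
| 5 | 0.3 | 33% | 39% |
| 5 | 0.5 | 41% | 28% |
| 4 | 0.3 | 31% | 27% |
| 4 | 0.5 | 39% | 20% |

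**Step 5: fewer measures, or more subjects**
- Three composites, each shifted by 1 SD, 8 per group: group-test power is 69%, 48% and 39% at ρ = 0, 0.3 and 0.5.
- Section 3 also gives 35 participants. At 17 v 18, error df = 33, so the 18-contrast test can be computed. Nine-measure group power for the uniform shift is then 84% (ρ = 0.3) or 64% (ρ = 0.5).

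**The case against.** The strongest reply is that Section 14 plans to look for redundancy and combine measures before any MANOVA. With seven or fewer combined measures the test exists. That is correct, and it limits the point: the defect is the absence of a number or rule, not an impossibility in principle. As written, nothing ensures that seven or fewer will result.

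Several stronger readings are tempting, and the documents do not support them:
- *The MANOVA as a whole cannot be run.* The nine-measure group test and the averaged interaction test both can, and the plan does not say which form it means.
- *The group test is singular too.* Entering the eight PDQ-39 aspects plus one measure for each other class would give 8 + 8 = 16 > 14. But the protocol says only what the questionnaire covers ("It contains thirty nine questions, covering eight aspects of quality of life"), not that eight scores enter the MANOVA.
- *Power is 16% to 23% whatever is assumed.* That holds for ρ of about 0.3 to 0.5. The range for the same shift is 67% to 12%.
- *A shift on all nine measures is the best case.* Under positive correlation it is an unfavourable pattern for Hotelling's test and an ideal one for an average score. With four or five measures moving, the advantage of the average score shrinks or reverses.
- *The trial's conclusions rest on the MANOVA.* The univariate ANOVAs, or mixed models where data are missing, come first and do not depend on it.

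It is also fair to say that a single global score does not answer Section 2's three hypotheses separately, and that low power here reflects the sample size as well as the choice of test.

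**Conclusion.** The point holds in a limited form. At 8 per group, the standard doubly multivariate tests of session and group-by-session cannot be computed on nine measures, nor on the eight in Section 8, with complete or imputed data. This needs no assumption beyond the plan's own counts. Section 14 locates the difficulty in missing data alone and does not secure the seven or fewer measures required.

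That the nine-measure group test is weak rests on assumed values (alpha 0.05, 1 SD shifts, equal correlation). In every 8 v 8 case shown it is below 80%, from 67% at ρ = 0 to 12% at ρ = 0.8 for the uniform shift, and 33% to 41% for five of nine measures at ρ = 0.3 to 0.5.

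The conclusion on computability depends on N = 16. Section 14 supports that number, but the 35 in Section 3 must be reconciled with it. This is a should-fix point: a stated analysis fails in its standard form, but the univariate results stand without it.

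**What to change.** In both MANOVA sentences (observed and imputed data), state that the doubly multivariate test will not be run on all nine or more measures. Then choose one of two routes.

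1. **Keep a MANOVA on a short list.** Name the measures or composites in advance, without using outcome data by arm. Seven is the limit of computability at N = 16. About three, matching the spatiotemporal, kinematic and quality-of-life hypotheses, is preferable. State the form of MANOVA and, if it is the averaged form, the sphericity assumption.
2. **Replace it with one directional global test.** Use an O'Brien-type average of standardised or ranked change, with the direction of each measure fixed beforehand. Define which T1 condition is the baseline, since Section 4 has T1 measured both without orthoses and with the first set. Any permutation must follow the actual allocation: Section 3 describes matched groups and three chip colours for two groups, so unrestricted 8/8 relabelling cannot be taken for granted.

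Reconcile 8 per group with 35 participants first, and base the degrees of freedom on the result.

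The cost is a few sentences of SAP text and little code. Route 1 gives up breadth, and power remains modest (39% to 69% for the group test in the three-composite example). Route 2 loses power, possibly falling below the MANOVA, when only some measures move or some worsen. A change score from T1 to one later visit would also leave the other follow-up visit unused. The plan should state these limits.
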